11.4 STUDY RECORD RETENTION

All study documentation will be kept for a minimum of 3 years from the protocol defined end of study point. When the minimum retention period has elapsed, study documentation will not be destroyed without permission from the sponsor. All data will be stored in both hard and soft files. Hard files will include audio recording DVDs, any notes, consent forms and incentive acceptance sheets. This data will be saved in locked cupboards in the office premises with the key kept safe with the project manager. Soft files will include audio recordings, exel sheet observation data, analysis results and report. These files will be saved in password enables computer system with limited access.

11.5 END OF STUDY

The end of study is defined as the submission of the study report.

The Investigators or the co-sponsor(s) have the right at any time to terminate the study for clinical or administrative reasons.

The end of the study will be reported to the REC, and R+D Office(s) and co-sponsors within 90 days, or 15 days if the study is terminated prematurely. The Investigators will inform participants of the premature study closure and ensure that the appropriate follow up is arranged for all participants involved. End of study notification will be reported to the co-sponsors via email to [contact].

A summary report of the study will be provided to the REC within 1 year of the end of the study.

11.6 INSURANCE AND INDEMNITY

The co-sponsors are responsible for ensuring proper provision has been made for insurance or indemnity to cover their liability and the liability of the Chief Investigator and staff.

The following arrangements are in place to fulfil the co-sponsors' responsibilities:

- The Protocol has been designed by the Chief Investigator and researchers employed by the University and collaborators. The University has insurance in place (which includes no-fault compensation) for negligent harm caused

by poor protocol design by the Chief Investigator and researchers employed by the University.

- Sites participating in the study will be liable for clinical negligence and other negligent harm to individuals taking part in the study and covered by the duty of care owed to them by the sites concerned. The co-sponsors require individual sites participating in the study to arrange for their own insurance or indemnity in respect of these liabilities.
- Sites which are part of the United Kingdom's National Health Service will have the benefit of NHS Indemnity.
- Sites out with the United Kingdom will be responsible for arranging their own indemnity or insurance for their participation in the study, as well as for compliance with local law applicable to their participation in the study.

12 REPORTING, PUBLICATIONS AND NOTIFICATION OF RESULTS

12.1 AUTHORSHIP POLICY

Ownership of the data arising from this study resides with the study team.

ANNEX C- OBSERVATION TOOL

CLINICAL OBSERVATIONS (were the following parameters followed)	
1. History taking	Y/N
Cough	
Fast breathing	
Laboured breathing	
Fever	
Immunization	
Breastfeeding history	
Overcrowding	
Parental smoking/Household member smoking	
Air pollution (indoor cooking stove)	
Nutritional history	
Hygienic practices	
Family history of HIV	
2. Examination (Did the healthcare provider make the following necessary examinations apart from others)	
Temperature	
Respiratory rate counting for 1 minute	
Pallor	
Skin rash	
Examine lower chest in drawing	
Auscultate for wheeze or crepts	
3. Diagnosis (Did the healthcare provider make the correct diagnosis based on WHO guidelines)	
Cough with no fast breathing/chest in drawing: No pneumonia	
With fast breathing and/or chest in drawing : Pneumonia	
Pneumonia with any danger signs : Severe Pneumonia	
4. Management (Did the healthcare provider manage the case per the guidelines)	

No Pneumonia: Symptomatic treatment	
Pneumonia: Oral amoxicillin 40mg/kg/dose twice daily for three days	
Severe Pneumonia: For LHWs: First dose of oral antibiotic (amoxicillin) and referral to health facility and For BHUs: First dose of oral antibiotic (amoxicillin) and referral to rural health centre or tertiary care hospital For health facilities (public and private) : Parenteral ampicillin 50mg/kg IV 6 hourly for five days along with gentamicin 7.5mg/kg/ IM or IV for five days.	

SCORE: (Count the total number of Y and enter the value in the table below)

ACTIVITY OBSERVED	“ Y” SCORED	TOTAL
History Taking		12
Examination		6
Diagnosis		1
Management		1

OBSERVATION RESULT*:

ACTIVITY OBSERVED	SELECT THE APPROPRIATE RESPONSE
History Taking	Correct/partially correct/ incorrect
Examination	Correct/partially correct/ incorrect
Diagnosis	Correct/ Incorrect
Management	Correct/ Incorrect

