8.2 PROPOSED ANALYSES

Behavioural coding will be employed to prepare the data for analysis. This means that a predetermined code will be given to each variable against each category of observations (History, examination, diagnosis and treatment). Each variable will be answered as "Y" meaning yes, the task was accomplished and "N" meaning no, the task was not accomplished (section 6.1). Additionally, the responses will be labelled as correct, partially correct and incorrect for history taking and examination. If on history taking, the healthcare provider asks questions on all variables, then the responses will be labelled as correct and if any one variable is missed then the response is indicated as partially correct and in case less than 50% of the variables are asked about, then the responses will be labelled as incorrect. The same labels will be specified for the examination. In case of diagnosis and treatment, the labels will be specified as correct and incorrect only as there is no partially correct diagnosis and treatment regimens. The overall frequencies and percentages of these responses will be calculated and cross tabulated across the provinces.

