***RESULT CRITERIA:**

For history taking:

Correct: Score of 12

Partially correct: Score of <12 but >6

Incorrect: Score of <6

For Examination:

Correct: Score of 6

Partially correct: Score of <6 but >3

Incorrect: Score of <3

For Diagnosis:

Correct: 1

Incorrect: 0

For Management:

Correct: 1

Incorrect: 0

Any other pertinent information:

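### Annex C has the person completing the form count the Ys and pick the history and examination labels; the plan states no derivation from the items and gives no label at exactly half

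*Combined protocol and SAP*

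**What the plan says.** Section 2.2.1 names correct history taking and correct examination as the first two of four primary endpoints. Under sections 3.5 and 7 the data collector attends the visit and completes the tool within one hour, helped by the audio recording and the prescription.

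Annex C lists 12 history and 6 examination items, each answered Y or N. Below them it instructs the person completing the form to "Count the total number of Y and enter the value in the table below". A second table then asks that person to "SELECT THE APPROPRIATE RESPONSE" for each activity. The result criteria for history are "Partially correct: Score of <12 but >6" and "Incorrect: Score of <6"; for examination they are "Partially correct: Score of <6 but >3" and "Incorrect: Score of <3". *Correct* needs 12 of 12 or 6 of 6.

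Section 8.2 states that "the responses will be labelled as correct, partially correct and incorrect for history taking and examination", without saying who or what applies the label. Its lower cut-off is "in case less than 50% of the variables are asked about, then the responses will be labelled as incorrect". Frequencies and percentages of the labels are then cross-tabulated by province.

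Section 7.1 puts the questionnaire on tablets that reject incomplete forms, with paper copies as a fallback. Section 7.2 lists the visit checklist and the collector's initials or ID among the eCRF contents. It lists no score or label field and describes no check of a label against the items.

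**The concern.** For history and examination, the label should follow from Y/N answers already in the database. Having a person add them up and choose a label brings in tally errors that a derived variable would not have. The plan does not say which source prevails if the chosen label and the items disagree.

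The top category is sensitive to this, because a single item separates 12 from 11 and 6 from 5. At half marks the person choosing has no rule on the form. If the label is a required field, something must be entered, and the choice may vary by collector. Section 4.1 plans two collectors per location, so a habit of one collector would show up as a feature of that province, and differences between provinces are the secondary objective.

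**Working it through.** **Inputs.** Visits per location, from section 8.1: 6 LHW, 4 BHU, 4 RHC, 9 private and 9 public. Locations: 5. Items: 12 history and 6 examination (Annex C). The documents give no slip rate and no expected item frequencies, so both are assumed below.

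**The plan's own figure.** (6 + 4 + 4 + 9 + 9) × 5 = 32 × 5 = 160 visits, which reproduces the stated minimum.

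**The two labelling rules, score by score.** Section 8.2 is read as: all items correct; at least one missed, partially correct; under 50%, incorrect.

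| Activity | Score | Annex C | Section 8.2 |
|---|---|---|---|
| History | 12 | correct | correct |
| History | 7 to 11 | partially correct | partially correct |
| History | 6 | no label | partially correct |
| History | 0 to 5 | incorrect | incorrect |
| Examination | 6 | correct | correct |
| Examination | 4 to 5 | partially correct | partially correct |
| Examination | 3 | no label | partially correct |
| Examination | 0 to 2 | incorrect | incorrect |

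Annex C labels 12 of the 13 possible history scores and 6 of the 7 examination scores. Section 8.2 labels all 13 and all 7. The two rules agree wherever Annex C gives a label.

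**Size of tally or selection error.** History and examination labels: 160 × 2 = 320. At an assumed 1%, 320 × 0.01 = 3.2; at 5%, 320 × 0.05 = 16. This is a ceiling of about 3 to 16 labels. Under the 8.2 rule, a tally slip of one changes the label only between 12 and 11 or 6 and 5 for history, and between 6 and 5 or 3 and 2 for examination. Within one location, one changed label moves a percentage by 1/32 = 3.1 points.

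**Size of the undefined scores.** Assume independent items, each done with the same probability p.

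- History = 6: 924 × p⁶ × (1 − p)⁶. At p = 0.3 or 0.7 this is 0.079, or 12.7 of 160 visits. At p = 0.5 it is 0.226, or 36.1 visits.
- Examination = 3: 20 × p³ × (1 − p)³. At p = 0.3 or 0.7 this is 0.185, or 29.6 visits. At p = 0.5 it is 0.3125, or 50 visits.

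Outside 0.3 to 0.7 the shares are lower. Real items are unlikely to be independent or equally frequent, so these figures only illustrate that the gap could touch more visits than miscounting. They count visits with no Annex C label, not wrong labels: a collector who picks partially correct agrees with 8.2.

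**The case against.** The strongest defence is that 8.2 already implies derivation. It places labelling within preparation of the data for analysis, codes each variable Y or N, and states the rule in terms of those variables. On that reading the analyst labels from the items and the Annex C boxes are only a field summary. This is a fair reading, so the documents do not support an inference that the analysis will use the collector's chosen label. They do not exclude it either, and one sentence would settle the matter.

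Second, a reader might infer that all scoring is done by hand. That is certain only for the printed tool and the paper fallback. The tablet version may add up and label automatically, but no section says that it does.

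Third, a reader might infer that a program would produce the labels without error. As Annex C stands it would not: it would return nothing at history 6 or examination 3. The cut-offs must be aligned first.

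Fourth, a collector inclined to leniency can mark single items Y, and programmed labels would carry that forward. Collector and province would remain entangled with two collectors per location. This stands: derivation removes tally error and discretion over the label, not judgement at item level.

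Finally, the items are kept and the analysis is descriptive, so a wrong label can be corrected later and no test is invalidated. This stands too, and it keeps the point minor.

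**Conclusion.** The point holds for primary endpoints 1 and 2. Annex C asks for a count and a chosen label, no section says that these are derived from or reconciled with the items, and at one score in each activity the form gives the chooser no label while 8.2 does.

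The effect is small. The 3 to 16 labels are an upper limit on an assumed rate, and the stored items allow any of them to be recomputed. The undefined scores concern the split between partially correct and incorrect; neither rule makes half marks correct, so they should not move the percentage correct.

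A reader might extend the point to all four primary endpoints, but the documents do not support that. Diagnosis and management each have three lines on the form but a maximum score of 1. Which line applies depends on the child's true classification, and neither Annex C nor the eCRF list in section 7.2 shows a field for it. Those two labels cannot be derived from the listed items.

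**What to change.** 1. Align the Annex C result criteria with 8.2 and state the rule once: below 50% of items, incorrect; from 50% up to but not including all items, partially correct; all items, correct. For history this is 0 to 5, 6 to 11 and 12; for examination, 0 to 2, 3 to 5 and 6.
2. State in 8.2 that history and examination scores and labels are computed by program from the stored Y/N items, and that these computed labels are the ones analysed.
3. If the form keeps a collector-entered count or label, use it only as a check and list disagreements by collector ID, which the eCRF already holds. If those entries are dropped, the listing is dropped too.

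The cost is a corrected cut-off in Annex C, a sentence or two in 8.2, a short derivation program and, at most, a minor change to the form. No further data need to be collected.

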***RESULT CRITERIA:**

For history taking:

Correct: Score of 12

Partially correct: Score of <12 but >6

Incorrect: Score of <6

For Examination:

Correct: Score of 6

Partially correct: Score of <6 but >3

Incorrect: Score of <3

For Diagnosis:

Correct: 1

Incorrect: 0

For Management:

Correct: 1

Incorrect: 0

Any other pertinent information:

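### Annex C gives no label to a history score of exactly 6 of 12 or an examination score of exactly 3 of 6, where section 8.2 implies partially correct

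*Combined protocol and SAP*

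**What the plan says.** Section 2.2.1 lists correct history taking and correct examination as primary endpoints 1 and 2. Two places in the document turn the Y/N items into labels.

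- **Annex C, Result criteria.** History is correct at 12. The other two categories are "Partially correct: Score of <12 but >6" and "Incorrect: Score of <6". Examination is correct at 6, followed by "Partially correct: Score of <6 but >3" and "Incorrect: Score of <3".
- **Section 8.2.** A response is correct when every item is covered. The lowest category is set by a percentage: "in case less than 50% of the variables are asked about, then the responses will be labelled as incorrect". The middle category has its own, differently worded condition: "if any one variable is missed then the response is indicated as partially correct". Examination is labelled in the same way. The frequencies and percentages of the labels are then cross-tabulated by province.

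On the form itself, the instruction is to "Count the total number of Y and enter the value in the table below" and then, for each domain, to "SELECT THE APPROPRIATE RESPONSE". The data collector completes the tool within an hour of the visit (section 3.5). The tablet does not accept incomplete forms (section 7.1). There are two collectors per province (section 4.1).

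**The concern.** Annex C uses strict inequalities on both sides of the midpoint, so one attainable score in each domain falls into no category. Section 8.2 uses a one-sided cut at 50% and does cover that score. The document does not say which rule prevails, or whether the tabulated label is the one ticked on the form or one computed from the items.

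If the ticked label is tabulated, a collector with a history score of 6 or an examination score of 3 has to choose without a rule. With only two collectors per province, any difference in habit would be mixed into the comparison between provinces, which is the secondary objective (section 2.1.2). The documents do not show that collectors would differ, but nothing in the plan prevents it.

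The wording of section 8.2 is also loose. If missing any one item means exactly one, history scores 6 to 10 and examination scores 3 to 4 have no label there either. If it means at least one, it overlaps with the less-than-50% clause at history 0 to 5 and examination 0 to 2.

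**Working it through.** **Denominator.** Section 8.1 plans 6 + 4 + 4 + 9 + 9 = 32 observations in each of five locations, and 5 × 32 = 160. This reproduces the stated minimum. Annex C lists 12 history items and 6 examination items, matching its stated totals.

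**Every score under both rules.** Section 8.2 is read naturally: incorrect below 50%, correct at 100%, partially correct between.

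| Domain | Score | Annex C | Section 8.2 |
|---|---|---|---|
| History | 0–5 | incorrect | incorrect |
| History | **6** | **no label** | **partially correct** |
| History | 7–11 | partially correct | partially correct |
| History | 12 | correct | correct |
| Examination | 0–2 | incorrect | incorrect |
| Examination | **3** | **no label** | **partially correct** |
| Examination | 4–5 | partially correct | partially correct |
| Examination | 6 | correct | correct |

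The two rules agree on 12 of 13 history scores and 6 of 7 examination scores. The only failures are the two midpoints.

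**How often the midpoint could occur.** The documents give no item completion rates, so I assume a common probability *p* per item and independent items:

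- P(history = 6) = C(12,6) p⁶(1−p)⁶ = 924 p⁶(1−p)⁶
- P(examination = 3) = C(6,3) p³(1−p)³ = 20 p³(1−p)³

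For example, at p = 0.5 these are 924/4096 = 22.6% and 20/64 = 31.25%.

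| p | History = 6 | of 160 | Examination = 3 | of 160 |
|---|---|---|---|---|
| 0.1 or 0.9 | 0.049% | 0.08 | 1.46% | 2.3 |
| 0.2 or 0.8 | 1.55% | 2.5 | 8.19% | 13.1 |
| 0.3 or 0.7 | 7.93% | 12.7 | 18.5% | 29.6 |
| 0.4 or 0.6 | 17.7% | 28.3 | 27.6% | 44.2 |
| 0.5 | 22.6% | 36.1 | 31.25% | 50.0 |

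Per province of 32 visits, that is 0 to 7 for history and 0.5 to 10 for examination.

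**Allowing items to be correlated.** I used a beta-binomial with correlation 0.2, so a + b = 1/0.2 − 1 = 4.

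| Mean | History = 6 | Examination = 3 |
|---|---|---|
| 0.1 or 0.9 | 1.84% (3 of 160) | 4.12% (7 of 160) |
| 0.3 | 7.6% | 14.3% |
| 0.5 | 10.8% (17 of 160) | 19.0% (30 of 160) |

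**Effect on the reported share labelled incorrect.** Under independent items, this is the binomial cumulative probability up to 5 or up to 6 (history) and up to 2 or up to 3 (examination).

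| p | History: midpoint partial → incorrect | Examination: midpoint partial → incorrect |
|---|---|---|
| 0.1 | 99.9% → 100.0% | 98.4% → 99.9% |
| 0.3 | 88.2% → 96.1% | 74.4% → 93.0% |
| 0.5 | 38.7% → 61.3% | 34.4% → 65.6% |

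Each pair moves all midpoint visits from one label to the other, so it is the widest possible swing at that *p*.

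**The case against.** The strongest reply is that section 8.2 already supplies the missing rule. Exactly half is not less than half, so the midpoint is partially correct, and Annex C is merely silent there without assigning a different label. Section 8.2 also describes the labelling as part of preparing data for analysis, and the eCRF contents in section 7.2 refer only to the checklist items of section 6.1, so the three-way label may not be a mandatory tablet field. The tool is still to be pretested and finalised (section 3.6). The Y/N items and recordings are kept, so nothing is lost for good. Finally, the endpoints are worded as correct history and correct examination, and that category is identical in both places.

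Much of this stands. The correct category is untouched, the labels can be rebuilt from the items, and pretesting might catch the gap. The midpoint counts rest wholly on an assumed *p*, and no disagreement between collectors has been shown.

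It does not remove the point. Section 8.2 does not say that a computed label replaces the selected one, and Annex C does ask for a selection. Section 8.2 reports all three labels. Nothing commits pretesting to resolve this boundary, and the same strict inequalities in both domains would carry over into any electronic form built from Annex C.

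**Conclusion.** The concern holds. As written, Annex C leaves history 6 of 12 and examination 3 of 6 unclassified, and section 8.2, read naturally, puts both in partially correct. That follows from enumerating the scores and needs no assumption.

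The consequence is limited to the boundary between partially correct and incorrect for two of the four primary endpoints. Diagnosis and management are not involved. How many visits are affected depends on completion rates that the documents do not give: negligible for history if nearly all or nearly none of the items are done, and up to about 36 of 160 (history) or 50 of 160 (examination) at an item probability of 0.5 with independent items. Correlation of 0.2 lowers those maxima to about 17 and 30. Examination is the more exposed endpoint because it has only seven possible scores.

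This should be fixed before data collection. It does not threaten the study.

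**What to change.** 1. In Annex C, write history as correct 12, partially correct 6 to 11, incorrect 0 to 5, and examination as correct 6, partially correct 3 to 5, incorrect 0 to 2. This adopts the plan's own 50% cut.
2. In section 8.2, define partially correct as at least one item missed but at least 50% of items done, and keep less than 50% for incorrect.
3. State that the label is derived from the count of Y answers, in the eCRF or at analysis, and is not selected by the data collector.

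Every score from 0 to 12 and from 0 to 6 then has exactly one label, and the two sections agree throughout. The cost is four edited lines in Annex C, one reworded sentence in section 8.2 and one derived field. If some forms have already been completed, the same derivation can be applied to the stored items.
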